## **6.4           EFFICACY ANALYSES**

### **6.4.1        Primary Efficacy Endpoint**

The primary efficacy endpoint will be the proportion of patients who have no evidence of disease activity (NEDA), as per protocol defined events during a 96-week period. The 8 weeks MRI scan will be the baseline for MRI activity.

The definition of a protocol-defined event of disease activity is the occurrence of at least one of the following while on treatment with ocrelizumab:

- A protocol-defined relapse as defined in Section [4.5.4](#)
- 24 weeks confirmed disability progression based on increases in EDSS while on treatment with ocrelizumab
- A T1 Gd-enhanced lesion after Week 8
- A new and/or enlarging T2 hyperintense lesion on MRI after Week 8 compared to the Week 8 MRI scan.

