2.2.2 Secondary Efficacy Outcome Measures

The secondary efficacy endpoints are the following:

- Proportions of NEDA patients during the initial 24-week period and the initial 48-week period
- Time to first protocol-defined event of disease activity
- Change in EDSS from baseline to Week 96
- Proportion of patients who, over a 96-week period, have Confirmed Disability Improvement (CDI), CDP or stable disability (i.e. neither CDI nor CDP).
- Annualized rate of protocol-defined relapses at Week 96
- Time to onset of first protocol-defined relapse
- Time to onset of 24 weeks CDP
- Time to onset of first new and/or enlarging T2 lesion
- Total number of T1 Gd-enhanced lesions detected by brain MRI at Weeks 24, 48 and 96

- Change in total T2 lesion volume detected by brain MRI from Week 8 to Week 96
- Volume and number of new and/or enlarging T2 hyperintense lesions from Week 8 to Weeks 24, 48 and 96
- Change in T1 hypointense lesion volume from Week 8 to Weeks 48 and 96
- Percentage change in brain volume from Week 8 measured at Weeks 24, 48 and 96
- Percentage change in white matter volume from Week 8 measured at Weeks 24, 48 and 96
- Percentage change in cortical grey matter volume from Week 8 measured at Weeks 24, 48 and 96
- Change from baseline in cognitive performance at Week 48 and Week 96 as measured by the components of the Brief International Cognitive Assessment for Multiple Sclerosis (BICAMS)

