4.4 EFFICACY ANALYSIS

4.4.1 Primary Efficacy Endpoint

Protocol-defined event definition

The definition of a protocol-defined event of disease activity is the occurrence of at least one of the following individual events while on treatment with ocrelizumab:

- A protocol-defined relapse defined as an occurrence of new or worsening neurological symptoms attributable to MS. Symptoms must persist for > 24 hours and should not be attributable to confounding clinical factors (e.g., fever, infection, injury, adverse reactions to medications), and immediately be preceded by neurological stability for at least 30 days.
- 24-weeks CDP based on increase in EDSS while on treatment with ocrelizumab
- A new T1 Gd-enhanced lesion on MRI after week 8
- A new and/or enlarging T2 hyperintense lesion on MRI after week 8

The MRI activity will be calculated on the events starting from week 8 (baseline reset).

Patient without any of this protocol-defined event of disease activity will be considered as NEDA = Yes (no evidence of disease activity).

The primary endpoint, NEDA, as well as the related disease activities components and combinations listed below, will be evaluated on the mITT population based on the following analysis principles:

- Patients, who discontinued treatment prior week 96 due to death or lack of efficacy, will be considered as having evidence of disease activity at the time of treatment discontinuation (e.g NEDA="NO", Relapse="Yes" and CDP="Yes").
- Patients who discontinued treatment for reasons other than death or lack of efficacy with no evidence of disease activity at the time of early treatment discontinuation will be excluded from the analysis as their disease activity status cannot be ascertained.

This is further summarized in the table below:

Endpoint	Patients who discontinued treatment without related disease activities prior week 96 due to:	
	death or lack of efficacy	Other reason than death or lack of efficacy with no evidence of disease activity
NEDA	included with evidence of disease activity (NEDA=NO)	excluded
Relapse	included with evidence of disease activity (Relapse=Yes)	excluded

24-weeks CDP	included with evidence of disease activity (CDP="Yes")	
 • If discontinuation before confirmation, excluded • If discontinuation after confirmation, included when CDP="Yes"
T1 Gd-enhanced lesions after week 8	included with evidence of disease activity	excluded

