4.4.2.8 Time to onset of first new and/or enlarging T2 lesion

This endpoint will not be analyzed as the measurement of T2 lesion by MRI is only performed at week 24, 48 and 96, while the actual onset time can be very different from the MRI visit.

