4.4.2.9 Time to onset of first T1 Gd-enhanced lesion

This endpoint will not be analyzed as the measurement of T1 lesion by MRI is only performed at week 24, 48 and 96, while the actual onset time can be very different from the MRI visit.

4.4.2.10 Total number of T1 Gd-enhanced lesions detected by brain MRI at Weeks 24, 48 and 96

The analyses will include patients in the ITT population. Data from unscheduled assessments will not be included in this summary or analysis.

The following analyses will be presented:

- Number and percentage of patients having 0, 1, 2, 3, and greater than 1 and greater than 3 lesions at weeks 24, 48 and 96.
- Number and percentage of patients having 0, 1, 2, 3, and greater than 1 and greater than 3 lesions in total detected at week 24, 48 and 96.
- The unadjusted and adjusted rates of lesion occurrence at weeks 24, 48 and 96 and the unadjusted and adjusted rate combining week 24, 48, 96 will be calculated:
 - The unadjusted rate will be the ratio of the total number of T1 Gd-enhanced lesions divided by the total number of interpretable MRI scans at each visit.
 - The adjusted rate will be derived using a negative binomial model. The dependent variable in the model will be the total number of T1-Gd-enhanced lesions. The model will be adjusted for the following covariates:
 - disease duration
 - presence of T1 Gd-enhanced lesions at screening (Yes/No),
 - presence of relapses prior screening as per CRF (Yes/No)
 - number of previous DMTs (1, >1).

In order to account for patients potentially receiving varying numbers of brain MRI scans during the study, the log-transformed number of brain MRI scans received will be included in the model as an “offset”.

- For the analysis above using negative binomial model for adjusted rate, if the model doesn't converge due to a high number of zero T1 Gd-enhanced lesion counts, other models, such as logistic regression model will be considered based on the same baseline variables. Patients having zero T1 Gd-enhanced lesions (but not missing) up to withdrawal will be considered as not having an event.

- Histogram of the count (0, 1, 2, 3, >1, >3) of T1 Gd-enhanced lesions at Weeks 24, 48 and 96, and during all visits (Weeks 24, 48 and 96) combined will be produced.

A descriptive analysis on the number of T1 Gd-enhanced lesions at screening and week 8 will also be performed.

4.4.2.11 Change in total T2 lesion volume detected by brain MRI from Week 8 to Week 96

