The analyses will include patients in the ITT population.

Data from other unscheduled assessments will not be included in this summary or analysis.

Change and percentage change from week 8 in total T2 lesion volume detected by brain MRI will be summarized.

4.4.2.12 Volume and number of new and/or enlarging T2 hyperintense lesions at Week 24, 48 and 96

The analyses will include patients in the ITT population.

The number of new and/or enlarging T2 lesions at week 24, 48 and 96 will be calculated as the sum of the individual number of new and/or enlarging lesions at each visit. Data from other unscheduled assessments will not be included in this summary or analysis.

The volume of new/or enlarging T2 lesions will also be analyzed at week 24, 48 and 96.

The same analysis as total number T1-Gd enhanced lesions and will be provided for the number of new and /or T2 lesions and a summary descriptive will be provided for the volume of new/or enlarging T2 lesions.

4.4.2.13 Change in T1 hypointense lesion volume from Week 8 to Weeks 48 and 96

The analyses will include patients in the ITT population.

The volume of T1 hypointense lesions at week 8, 48 and 96 along with the change from week 8 to week 48 and to week 96 will be summarized descriptively. In addition, change and percentage change from Week 8 in T1 hypointense lesion volume detected by brain MRI at Weeks 48 and 96 will be analyzed using a longitudinal MMRM. These MMRM analyses will be undertaken using the same approach as described above in Section 4.4.2.3.

4.4.2.14 Percentage Change in brain volume from Week 8 measured at Weeks 24, 48 and 96

This endpoint will be analyzed on the ITT population.

Brain volume is recorded as an absolute “normalized” (refer to “Electronic Data File Format & Transfer Specifications”) value at week 8 (baseline reset) then recorded at subsequent visits as a percentage change relative to the normalized brain volume value

at week 8. Any volume measurement from the MRIs that were done after infusion at the same visit will not be included in the analysis, i.e., manually considering as missing. Same rule applies to cortical grey matter volume and white matter volume.

Percentage change in brain volume relative to Week 8, as detected by brain MRI scan, will be summarized at weeks 24, 48 and 96 using descriptive statistics. Data from other unscheduled assessments will not be included in this summary or analysis.

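### New or enlarging T2 lesions are analysed per scan although the scan gaps are 16, 24 and 48 weeks, so constant disease activity would appear as a 1 : 1.5 : 3 rise by visit

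*SAP*

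**What the plan says.** SAP 2.2.2 lists the secondary endpoint as "Volume and number of new and/or enlarging T2 hyperintense lesions from Week 8 to Weeks 24, 48 and 96". SAP 4.4.2.12 says the number of lesions "will be calculated as the sum of the individual number of new and/or enlarging lesions at each visit", and then: "The same analysis as total number T1-Gd enhanced lesions and will be provided for the number of new and /or T2 lesions".

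The imported analysis is in SAP 4.4.2.10. The unadjusted rate is the lesion total over the number of interpretable scans. For the adjusted rate, a negative binomial model is used in which "the log-transformed number of brain MRI scans received will be included in the model as an" offset. Both are given at Weeks 24, 48 and 96 and for the three visits combined.

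The schedule of assessments places brain MRI at screening and Weeks 8, 24, 48 and 96, with none at Week 72, plus a scan at early treatment discontinuation. SAP 4.4.2.8 drops the time-to-first-T2-lesion endpoint because "the measurement of T2 lesion by MRI is only performed at week 24, 48 and 96" and onset may lie well away from the visit. For relapses, the other count that builds up over time, SAP 4.4.2.5 uses log years of exposure as the offset. No section adjusts the T2 rate for interval length.

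**The concern.** An enhancing lesion is either visible on the day of the scan or not, so lesions per scan is a sensible rate whatever the spacing. A new or enlarging T2 lesion is defined by comparison with an earlier scan, so the expected count grows with the time between the two. Dividing by scans treats 16 weeks and 48 weeks of accumulation as equal exposure.

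Protocol 1.2 reports T2 lesions per scan from the two randomised Phase III trials in relapsing MS, but as relative reductions between arms. With a shared schedule the unequal gaps largely cancel in such a ratio. This trial has one arm and reports absolute rates over time, so they do not cancel. A reader who sees the T2 rate climb from Week 24 to Week 96 could take it for waning control when it reflects only the schedule. The combined rate is also exposed to who left early and who missed a scan, since both change the number of weeks behind each scan.

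**Working it through.** The documents give no expected rate or precision for this endpoint, so there is no stated figure to reproduce.

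**Inputs.** Reference scan at Week 8; later scans at Weeks 24, 48 and 96; windows of ±3 days at Week 8 and ±14 days at the others (schedule of assessments). Each count is taken to be against the previous scan. This is implied twice: SAP 4.4.2.12 adds the visit counts, and sensitivity analysis B in SAP 4.4.4, which uses a screening baseline, obtains the Week 24 number by adding the Week 8 and Week 24 counts. Neither sum makes sense otherwise.

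**By-visit rates.** With constant activity of λ lesions per week, expected lesions per scan = λ × weeks since the previous scan.

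| Visit | Interval (weeks) | Range under visit windows | Per scan if activity is 0.5 per 48 weeks |
|---|---|---|---|
| Week 24 | 24 - 8 = 16 | 13.6 to 18.4 | 0.167 |
| Week 48 | 48 - 24 = 24 | 20 to 28 | 0.250 |
| Week 96 | 96 - 48 = 48 | 44 to 52 | 0.500 |

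The ratio is 16 : 24 : 48 = 1 : 1.5 : 3. At a single visit every patient contributes one scan, so the offset is log(1) = 0 and the model does not remove the pattern. The visit windows do not remove it either.

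**Combined rate.** A patient with all scans has 88/3 = 29.3 weeks per scan. Across patients, the unadjusted rate = λ × (mean weeks covered) / (mean number of scans). Two assumed cases:

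- 10% leave after Week 24 and 10% after Week 48: weeks = 0.10×16 + 0.10×40 + 0.80×88 = 76.0; scans = 0.10×1 + 0.10×2 + 0.80×3 = 2.7; 76.0/2.7 = 28.1, and 28.1/29.3 = 0.96.
- No dropout, 10% missing at each of Weeks 24 and 48: 88/(3 - 0.2) = 31.4, and 31.4/29.3 = 1.07.

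The negative binomial model was checked by simulation: 200,000 patients per scenario, constant 0.5 lesions per 48 weeks, dispersion 2, no covariates. These settings and the missingness levels are assumptions, not taken from the documents.

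| Assumed pattern | Scan offset, relative to complete data | Time offset (true value 0.50 per 48 weeks) |
|---|---|---|
| Dropout 3% + 4% (after Week 24 + after Week 48) | -2% | 0.500 |
| Dropout 5% + 10% | -4% | 0.499 |
| Dropout 10% + 10% | -6% | 0.496 |
| 5% missed at each of Weeks 24 and 48 | +4% | 0.497 |
| 10% missed at each | +9% | 0.499 |
| Dropout 5% + 10% with 5% missed | about 0% | 0.502 |

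The missed-scan rows assume that the scan after a miss is read against the last available scan. With log time from Week 8 to the last scan as offset, the rate stays within about 1% of the truth throughout.

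**The case against.** Lesions per scan at these weeks is the metric reported for the earlier Phase III trials, and the rationale for Amendment 5 says the statistical section was changed partly to align with the ocrelizumab programme. That is a good reason to keep per-scan figures for comparison, but not to use them as the rate over time in a single-arm trial.

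The analysis is exploratory and mainly descriptive (Protocol Section 6). This is one secondary MRI endpoint, and outputs are labelled by week, so an attentive reader could allow for the schedule. This stands and limits the weight of the point.

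The effect of missed scans rests on a reading rule that the documents do not contain. Scans are read centrally, with details in a separate technical manual (Protocol 4.5.7). The SAP also does not say whether the early-discontinuation scan enters the count. Both stand, which is why the combined-rate figures are conditional.

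Two stronger readings are tempting:

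- From the SAP 2.2.2 wording, and from the protocol's event "A new and/or enlarging T2 hyperintense lesion on MRI after Week 8 compared to the Week 8 MRI scan", a reader might infer that every visit count is against Week 8, so that adding the visits counts early lesions repeatedly. The documents do not support this. The protocol text defines the yes/no NEDA event, SAP 2.2.2 gives an endpoint window, and the protocol's own count endpoint (Section 2.1.2) runs from baseline. The two sums in SAP 4.4.2.12 and 4.4.4 point to the previous scan.
- A reader might compare weeks per scan between a patient who leaves early and one who misses a middle scan, and take that gap as the bias in the result. It is not the bias of any reported estimate. Patients with all scans share 29.3 weeks per scan, and the pooled shift is a few percent.

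**Conclusion.** The point holds. The by-visit T2 rates would show a 1 : 1.5 : 3 rise under constant activity with complete data, provided counts are against the previous scan, which the SAP implies but does not state. That part is large and needs no assumption about missing data.

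The distortion of the combined rate is secondary: about -6% to +9% under the assumed patterns, with dropout and missed scans pulling in opposite directions and able to offset each other. It further assumes that the scan after a miss is read against the last available one.

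Binary NEDA uses presence or absence of a lesion, so the primary result is not affected. The change should be made before the T2 rates are produced, but nothing here threatens the trial's main conclusion.

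**What to change.** In SAP 4.4.2.12:

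1. State that each count is against the previous evaluable scan, and confirm this against the central reading rule, including what happens after a missed scan and whether the early-discontinuation scan counts.
2. For the combined rate, replace the scan-number offset with log time from the Week 8 scan to the last evaluable scan.
3. Report by-visit results as lesions per year over the interval since the reference scan. In the example above all three visits then give the same value: (0.5/48) × (365.25/7) = 0.54 per year.
4. Keep the per-scan figures as a descriptive comparison with the earlier trials, labelled as such and with the interval lengths shown.

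SAP 4.4.3.5 sends the T2 totals up to Weeks 24 and 48 to the same Gd-lesion analysis and should follow the change.

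The cost is SAP wording and one time variable built from scan dates, with no new visits or scans. If central reading turns out to use a different reference, the derivation or the data transfer may also need to change; the documents cannot settle that. The downside is that the main T2 figure is no longer directly per scan, which item 4 covers.

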4.4.3 Exploratory Efficacy Endpoints

Exploratory efficacy endpoints include patient-reported outcomes (PROs) related to health-related quality of life (QoL), treatment satisfaction and other clinical endpoints. Summaries for change from baseline in these exploratory efficacy endpoints at Weeks 24, 48 and 96 will be provided.

In addition to the model based analyses, all PRO exploratory endpoints will be summarized descriptively at each assessment visit for individual question or domain as well as total scores as appropriate.

4.4.3.1 Multiple Sclerosis Impact Scale (MSIS)-29

The MSIS-29 v2 is a 29-item PRO designed to measure the physical and psychological impact of MS. Items are rated on a 4-point likert scale and are summed for each domain. These summed scores are transformed for ease of interpretability. Lower transformed scores correspond to better HRQoL.

Domain	Items #	Item Scores	Domain score
--------	---------	-------------	--------------

Physical Scale	1-20	1 = Not at all 2 = A little 3 = Moderately 4 = Extremely	Sum of items 1-20, see below for missing data handling
Psychological Scale	21-29	1 = Not at all 2 = A little 3 = Moderately 4 = Extremely	Sum of items 21-29, see below for missing data handling

A transformed score will be calculated from each domain score, respectively

	Calculation for transformed score	Range
Physical Scale	$[(\text{domain score}-20)/(80-20)]*100$, see below for missing data handling	0-100
Psychological Scale	$[(\text{domain score}-9)/(36-9)]*100$, see below for missing data handling	0-100

Missing data handling:

- Respondents must have a minimum of 10 completed items in the physical scale, or a minimum of 5 completed items in the psychological scale in order to use the imputing process above to impute the missing individual items
- Missing scores in the specific scale are imputed as the average of the scores of all (completed) items in that scale. For example, if a patient has completed 15 items (item 1-15) in the physical scale and the values for item 16-20 are missing. Then first sum the completed items 1-15 and then divide by 15 to get his respondent-specific mean score. Then use this value as the score for each of the missing 5 items 16-20. Then generate a total score as usual by summing the values of the 15 completed items 1-15 and the 5 imputed items 16-20 based on the score calculation for physical scale above.

For any analyses of domain scores, transformed domain scores will be used as they have range of 0-100 and intuitive to understand.

A summary table will present, by visit, the number of patients with:

- All items completed in the physical scale
- A minimum of 10 completed items in the physical scale
- All items completed in the psychological scale
- A minimum of 5 completed items in the psychological scale

The mean change in the physical and psychological MSIS-29 v2 domain scores from baseline to weeks 24, 48 and 96 will be summarized descriptively.

4.4.3.2 Treatment satisfaction questionnaire for medication (TSQM II)

The TSQM II consists of 11 questions and 4 domains. Scores are rated on a 5 – or 7-point likert scale. Items within a domain are summed and then transformed to a 0 – 100 scale, where a lower score corresponds to lower satisfaction.

Domain	Item #	Item Score	Transformed Domain Score	Range
--------	--------	------------	--------------------------	-------

Effectiveness	1-2	1 = Extremely Dissatisfied 2 = Very Dissatisfied 3 =Dissatisfied 4 = Somewhat Satisfied 5 = Satisfied 6 = Very Satisfied 7 = Extremely Satisfied	$\frac{((\text{Items \#1} + \text{\#2}) - 2)}{12} * 100$ If one item is missing: $\frac{((\text{Use the completed item})) - 1}{6} * 100$	0-100
Side Effects	3	1 = Yes 0 = No*	All 'not applicable' responses in items #4 – #6 will be scored as 5 for the derivation of the side effect domain score	
	4-6	1 = Extremely Dissatisfied 2 = Very Dissatisfied 3 = Somewhat Dissatisfied 4 = Slightly Dissatisfied 5 = Not at all Dissatisfied	$\frac{([\text{Sum}(\text{Items \#4, \#5, \#6}) - 3]}{12} * 100$ If one item is missing: $\frac{([\text{Sum}(\text{the two completed items})) - 2]}{8} * 100$	0-100
Convenience	7-9	1 = Extremely Dissatisfied 2 = Very Dissatisfied 3 =Dissatisfied 4 = Somewhat Satisfied 5 = Satisfied 6 = Very Satisfied 7 = Extremely Satisfied	$\frac{([\text{Sum}(\text{Items \#7, \#8, \#9}) - 3]}{18} * 100$ If one item is missing: $\frac{([\text{Sum}(\text{the two completed items})) - 2]}{12} * 100$	0-100
Global Satisfaction	10-11	1 = Extremely Dissatisfied 2 = Very Dissatisfied 3 =Dissatisfied 4 = Somewhat Satisfied 5 = Satisfied 6 = Very Satisfied 7 = Extremely Satisfied	$\frac{([\text{Item \#10} + \text{\#11}) - 2]}{12} * 100$ If one item is missing, then Domain score is missing	0-100

* note, if response to item #3 is "No", questions # 4, #5 and #6 are "not applicable"

A summary table will present, by domain and visit, the number of patients with all items completed.

Each TSQM II transformed domain score will be summarized descriptively by visit. No imputation of missing data will be performed. This analysis will be repeated on the last DMT prior to study enrollment subgroup.

The mean change in each TSQM II transformed domain score from baseline to weeks 24, 48 and 96 will be summarized descriptively for completers only.

A separate analysis on the answer to Question 3: "As a result of taking this medication, do you experience any side effect at all?" will be performed. A shift table (cross tabulate) on the answer will be present from baseline to week 24, 48 and 96. These two analyses will be repeated on the last DMT prior to study enrollment subgroup.

